² If clinical signs suggesting brain metastases (performed within 2 weeks before registration at most), or if known brain metastases

³ According to the investigator judgment

⁴ In case of first progression in patient with lung cancer and sarcoma. A chest and abdominal CT scan has to be performed 6 weeks after the second SABR course.

⁵ With a window of ± 3 days allowed for the beginning of the stereotaxy. The full treatment should not last more than 8 days long

- * within 28 days before treatment no specific treatments will be allowed (washout period); the maximum duration for the screening period is 28 days.
- ** Patients who discontinue atezolizumab for disease progression will have an end of study visit 1 month after treatment discontinuation.

Patients who discontinue atezolizumab for other reason than disease progression will have a follow-up visit every 3 months up to 12 months or disease progression according to RECIST 1.1, whichever occurs first.

*** Archival tumour sample, biopsy at baseline (before Atezolizumab treatment), at week 4 or up to 8 days before C2D1 (i.e before start of SABR), at week 7 or up to 8 days before C3D1 (after atezolizumab and SABR combination). Only tissue from core needle, punch or excisional biopsy sample collection will be accepted. For core-needle biopsy specimens, three cores should be submitted for evaluation. Fine-needle aspiration, brushing, bone tissue, and lavage samples are not acceptable

ABREVIATIONS

AE Adverse event

AESI Adverse event of special interest

ALK Alkaline phosphatase
ALT Alanine transaminase

aPTT Activated Partial Thromboplastin Time

AST Aspartate aminotransferase

BCC Basal Cell Carcinoma

BED equivalent biologic dose

CBC Complete Blood Count

CHO Chinese hamster ovary

CL Clearance

CR Complete response

CRA Clinical Research Assistant

CRC Colorectal cancer
CRF Case Report Form
CRP C-Reactive Protein

CT Computed tomography
DCR Disease Control Rate
DOR Duration of response

EC Ethic committee
ECG Electrocardiogram

ECOG Eastern Cooperative Oncology Group

FDG [18F]-fluorodeoxyglucose

GI Gastrointestinal
GR Gustave Roussy
HBV Hepatitis B virus

HCG Hormon chorionic gonadotropin

HCV Hepatitis C virus

HIV Human immunodeficiency virus

IB Investigational Brochure
ICF Informed consent form

ICH International conference of harmonization

IFN-α interferon-α

Ig Immunoglobulin

IL-2 interleukin-2

IMP Investigational Medicinal Product

INR International Normalized Ratio

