5.1.2 Stereotactic Ablative Radiation Therapy (SABR)

SABR will be administered concurrently during the second cycle of the anti-PD-L1 Atezolizumab (week 4) and in case of first progression in patients with lung cancer and sarcoma.

SABR will be delivered using 6MV photons or other energies with standard field encompassing tumour. Hypofractionated SABR will be delivered within 3 fractions in total to a total of 45 Gy (3 fractions of 15 Gy). In order to comply with the QUANTEC normal tissue tolerance guidelines, the dose may be adapted according to dosimetric constraints but must never be inferior to 33 Gy in fractions of 11 Gy.

Tumour size will be ≤ 4 cm according to recent imaging (CT, MR or PET).

The radiation dose will be prescribed to the 90% isodose line in order to deliver 95% of the planned dose to 95% of the planned tumour volume (PTV).

Patients will be eligible if dose constraints to organ at risk are respected.

SABR software tools and accurate dose calculations allow for better targeting of tumours, while providing motion management for precise dose delivery. Generally, this technique includes:

- 4D CT data integration for moving target such as lung tumours
- Patient's immobilization with a vacuum cushion.
- Precise type B dose calculation algorithm (Monte Carlo, or other type B dose calculation algorithms)
- Monitoring of respiratory motion.
- Real-time detection and compensation of tumour motion (on-board CT)

The definition of volumes will be in accordance with ICRU Reports #50, #62 and #83.

SABR will be given on alternate days and only type B dose calculation algorithms will be accepted.

Margins from GTV (or ITV) to PTV are of 5 - 10 mm to account for set-up error and organ motion.

Any organ that is traversed by part or all of a beam should be contoured so that the dose it receives can be assessed. Organs should be outlined by the treating radiotherapist (or dosimetrist and checked by treating radiotherapist). Dose constraints are adapted to the standard recommendations (cf Appendix 1: Rules for SABR administration according to tumour location).

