5.2 Dosage and schedule of treatment

5.2.1 Atezolizumab

The dose of atezolizumab will be 1200 mg administered by intravenous infusion every 3 weeks (21 [+ 3] days).

Administration of atezolizumab will be performed in a setting with emergency medical facilities and staff who are trained to monitor for and respond to medical emergencies.

The initial dose of atezolizumab will be delivered over $60 (\pm 15)$ minutes. If the first infusion is tolerated without infusion-associated adverse events, the second infusion may be delivered over $30 (\pm 10)$ minutes. If the 30-minute infusion is well tolerated, all subsequent infusions may be delivered over $30 (\pm 10)$ minutes.

For the infusion, the patient's vital signs (heart rate, respiratory rate, blood pressure, and temperature) should be determined within 60 minutes before, and 30 (\pm 10) minutes and after the infusion. For subsequent infusions, vital signs will be collected within 60 minutes before infusion and at the end of the infusion, if clinically indicated.

Patients will be informed about the possibility of delayed post-infusion symptoms and instructed to contact their study physician if they develop such symptoms.

No premedication will be allowed for the first dose of atezolizumab. Premedication may be administered for Cycles ≥ 2 at the discretion of the treating physician. The management of infusion-related reactions will be performed according to severity as described in section 5.3.2.6

In the event of a suspected anaphylactic reaction during study drug infusion, the following procedures should be performed:

- Stop the study drug infusion
- Apply a tourniquet proximal to the injection site to slow systemic absorption of study drug. Do not obstruct arterial flow to the limb.
- Maintain an adequate airway
- Administer antihistamines, epinephrine or other medications as required by patient status and directed by the physician in charge
- Continue to observe the patient and document observations

Guidelines for dosage modification, treatment interruption or discontinuation, and the management of specific adverse events are provided 5.3.2.

Any overdose or incorrect administration of study drug should be noted on the Study Drug Administration Case Report Form (CRF). AEs associated with an overdose or incorrect administration of study drug should be recorded on the Adverse Events CRF pages.

Cessation of immunotherapy for long-term responders

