7.2 Secondary criteria

7.2.1 Efficacy

- Progression-free survival (PFS) measured from the date of treatment initiation to the date of progression or death, whichever comes first. Patients alive and free of progression at the cut-off date will be censored at the last assessment date.
- Modification of the size of the irradiated and non irradiated lesion(s) as measured by its longest diameter according to RECIST 1.1 will be compared.

Assessment of efficacy endpoint listed below will be performed according to RECIST v 1.1 criteria (refer to Appendix 4: RECIST 1.1 CRITERIA) and modified RECIST (mRECIST) (refer to Appendix 5: mRECIST CRITERIA MODIFIED RESPONSE EVALUATION CRITERIA IN SOLID TUMORS).

Efficacy endpoints are:

- Disease Control Rate (DCR): complete responses (CR) + partial responses (PR) + stable disease (SD).
- Objective Response Rate (ORR): CR + PR
- Duration of response (DOR)
- Time to progression (TTP) of non irradiated lesions is computed as the delay from enrollment to the first occurrence of progression outside of the irradiated field
- Time to progression (TTP) of irradiated lesions is computed as the delay from enrollment to the first occurrence of progression of irradiated lesions;
- Evaluation of the local control, distant control.

In lung cancer and sarcoma patients receiving a second SABR course:

For patients in lung and sarcoma cohorts who can receive a second SABR course if oligoprogression, the objective response rate at 6 weeks is defined as any partial or complete response according to RECIST v1.1 observed at the first radiological evaluation (6 weeks after the second SABR course) over the number of patients that received a second SABR course.

- Size of the irradiated and non irradiated lesion(s) is measured in its longest diameter according to RECIST 1.1. Modification observed between the time of progression 1 and the value at 6 weeks will be compared between irradiated and non irradiated lesions.

- Progression-free survival 2 (PFS2) measured from the date of the second SABR course to the date of second progression or death. Patients alive and free of progression at the cutoff date will be censored at the last assessment date.
- Time to progression ratio (TTPr) in patient that received a second SABR course. To define the TTP ratio, let's denote:
 - o TTP1 the time from treatment initiation to the time of progression after first irradiation

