8.3.2 Efficacy Analysis

Progression free survival (PFS) is defined as the time from treatment initiation to first documentation of tumour progression or to death, whatever the cause of death, whichever occurs first. Any patient that discontinues due to a reason other than progressive disease (for example, AE, patient/investigator decision) will have their time-to-event data either censored at

the follow-up visit if no progressive disease is found during this visit, or censored at the date of the last objective progression-free disease assessment if progressive disease is found at the follow-up visit. The progression will be assessed using RECIST v 1.1 and mRECIST.

Time to progression of non irradiated lesions is computed as the delay from enrollment to the first occurrence of progression outside of the irradiated field. Time to progression of irradiated lesions is computed as the delay from enrollment to the first occurrence of progression of irradiated lesions.

The disease Control Rate (DCR) will be defined as the sum of complete responses (CR), partial responses (PR) and stable disease (SD). The objective Response Rate (ORR) will be defined as the sum of complete responses (CR) and partial responses (PR).

The PFS, DCR, ORR and DOR will be computed by patient. In each cohort, response rates with exact 95% confidence intervals will be provided, and PFS and duration of response will be estimated using Kaplan-Meier survival method and presented with Rothman's 95% Confidence Intervals. Median follow-up will be estimated using inverse Kaplan-Meier method (Collet D., 1994). Secondary analysis will investigate the impact of the number of metastatic sites in 2 modalities (<5 and ≥5). A semi-parametric Cox model stratified on the cohort and adjusted for the number of metastasis will be developed.

The TTP ratio (TTPr) will be computed in all patients receiving a second SABR course, as the ratio of TTP2 over TTP1. Patients receiving a second SABR course without a documented progression 1 will not be included. Patients dying without documented second progressions will be counted as progressions at the date of death considering the very poor prognosis of those patients. Censored TTP2 will make the TTPr censored too. In this case, the Kaplan-Meier approach will be used to derive values of TTPr. For instance, rate of patients with TTPr greater than 1.5 will be computed, among other thresholds (1.33, 1.5, 2).

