20 APPENDIX 4: RECIST 1.1 CRITERIA

The criteria below are based on RECIST 1.1. (Eisenhauer EA et al.Eur J Cancer 2009;45:228-247)

Measurability of the disease

Measurable disease: Measurable disease requires the presence of at least one measurable lesion. If the measurable disease is restricted to a solitary lesion, its neoplastic nature should be confirmed by cytology/histology.

Measurable lesions:

- Lesions that can be accurately measured in at least one dimension with longest diameter ≥ 10 mm (by CT scan, MRI, caliper measurement) or ≥ 20 mm (by chest X-ray). Longest diameter will be recorded.
- For a lymph node to be considered pathologically enlarged and measurable, the short axis must be ≥15 mm (by CT scan). The short axis will be recorded.

Non-measurable disease:

- Non-measurable lesions are all other lesions, including small lesions (longest diameter <10 mm with CT scan, MRI or caliper measurement or <20 mm with chest X-ray or pathological lymph nodes with shortest axis ≥10 and <15 mm) as well as truly non-measurable lesions. Lesions considered truly non-measurable include leptomeningeal disease, ascites, pleural or pericardial effusion, inflammatory breast disease, lymphangitic involvement of skin or lung, abdominal masses/abdominal organomegaly identified by physical exam that is not measurable by reproducible imaging techniques.

- New lesions in irradiated fields
- Previously irradiated lesions should not be used as indicator lesions. However, new lesions occurring in previously irradiated fields can be used to assess the anti-tumour response.

Methods of measurement

All measurements must be recorded in metric notation, using a ruler or calipers. All baseline evaluations must be performed as close as possible to the treatment start and within 4 weeks before the beginning of the treatment. If a lesion is considered too small to measure, a default measurement of 5 mm should be applied. If the lesion is not visible, a default measurement of 0mm should be applied.

The same method of assessment and the same technique must be used to characterise each identified and reported lesion at baseline and during follow-up.

Clinical lesions will only be considered measurable when they are superficial (e.g., skin nodules, palpable lymph nodes). In the case of skin lesions, documentation by colour photography including a ruler to estimate the size of the lesion is suggested.

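### Both lesion-level times to progression start at enrollment while PFS starts at treatment initiation, which can add up to 28 untreated days that vary by patient

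*Protocol*

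**What the plan says.** The origin is fixed in three places: the synopsis (secondary evaluation criteria), Section 7.2.1 and Section 8.3.2. For irradiated lesions, Section 7.2.1 says that TTP "is computed as the delay from enrollment to the first occurrence of progression of irradiated lesions", and Section 8.3.2 reads "Time to progression of irradiated lesions is computed as the delay from enrollment". For non-irradiated lesions TTP "is computed as the delay from enrollment to the first occurrence of progression outside of the irradiated field".

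Other time-to-event measures start elsewhere. The primary rate (Section 7.1) and PFS (Sections 7.2.1 and 8.3.2) run from treatment initiation. So does TTP1 in the evaluation criteria, although the synopsis objectives start TTP1 at inclusion. PFS2 runs from the second SABR course.

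On timing, the notes to Table 1 state that "the maximum duration for the screening period is 28 days", and this note is attached to the enrolment column. Section 5.1.2 places the first radiotherapy course at cycle 2: "SABR will be administered concurrently during the second cycle of the anti-PD-L1 Atezolizumab (week 4"). Section 6.2 schedules CT at weeks 4, 7 and 13 and then every 12 weeks. Appendix 4 asks for baseline measurements "as close as possible to the treatment start and within 4 weeks before the beginning of the treatment" and judges progression against the smallest sum on study, which may be that baseline. No new reference is set at SABR.

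**The concern.** A lesion-level TTP is read next to PFS. Where a patient's first progression is in a non-irradiated lesion, the two endpoints record the same event on the same scan, and on a common clock they should agree. As written, TTP is longer by the interval from enrollment to first dose. That interval reflects scheduling, not disease or treatment, and it differs between patients, so a constant cannot be subtracted to remove it.

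For irradiated lesions there is a second layer. The clock also covers about three weeks of atezolizumab before any radiation, while the size reference dates from before treatment. The number then mixes time before and after SABR, and a reader who takes it as the time a lesion stayed controlled after radiotherapy would misread it. Describing efficacy on irradiated and non-irradiated lesions is a stated secondary objective, so these times are likely to be reported.

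**Working it through.** The protocol gives no median, rate or sample size for lesion-level TTP, so there is no figure of its own to reproduce.

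**Inputs**
- Enrollment to first dose: 0 to 28 days (Table 1 notes), if enrollment opens screening.
- First dose to SABR at week 4: 21 days nominal. Section 5.2.1 gives the cycle as "every 3 weeks (21 [+ 3] days"), and Table 1 adds "With a window of ± 3 days allowed for the beginning of the stereotaxy".

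**Step 1: lead-in before SABR.** Nominal: 0 + 21 = 21 days to 28 + 21 = 49 days (3 to 7 weeks). With both windows: 0 + 21 − 3 = 18 days to 28 + 24 + 3 = 55 days (2.6 to 7.9 weeks).

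**Step 2: one event on two clocks.** PFS time = scan date − first dose. TTP = PFS time + (0 to 28 days).

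| Progression seen at | From treatment initiation | From enrollment |
|---|---|---|
| Week 4 | 21 days | 21 to 49 days |
| Week 7 | 42 days | 42 to 70 days |
| Week 13 | 84 days | 84 to 112 days |

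This step needs no model. Against the treatment-initiation clock, the enrollment clock is never shorter and can be up to 28 days longer.

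**Step 3: lead-in alone, irradiated lesions.** Assume a constant hazard starting at SABR, median m weeks (an assumption), and no events before SABR. With lead-in g weeks, the reported median is m + g and the progression-free share at t is exp(−ln 2 × (t − g)/m). From treatment initiation g = 3; from enrollment g = 3 to 7.

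| Assumed median from SABR | From treatment initiation | From enrollment | Excess of enrollment clock over SABR clock | 52-week share: SABR / initiation / enrollment |
|---|---|---|---|---|
| 13 wk | 16 wk | 16–20 wk | 23–54% | 0.062 / 0.073 / 0.073–0.091 |
| 26 wk | 29 wk | 29–33 wk | 12–27% | 0.250 / 0.271 / 0.271–0.301 |
| 52 wk | 55 wk | 55–59 wk | 6–13% | 0.500 / 0.520 / 0.520–0.549 |
| 104 wk | 107 wk | 107–111 wk | 3–7% | 0.707 / 0.721 / 0.721–0.741 |

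As a rate: with an assumed 80% progression-free at 6 months (182.6 days) after SABR, the enrollment clock reads 0.80^((182.6 − 21)/182.6) = 0.82 to 0.80^((182.6 − 49)/182.6) = 0.85.

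**Step 4: the opposing effect.** For volume doubling time V (an assumption), diameter grows by 2^(d/(3V)) − 1 in d days. For V = 60, 90, 120 and 180 days this is 8.4, 5.5, 4.1 and 2.7% in 21 days, and 20.8, 13.4, 9.9 and 6.5% in 49 days. Measured against a pre-treatment baseline, such growth uses up part of the 20% progression threshold, or all of it at the extreme, before any radiation. This shortens TTP.

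**The case against.** Four counter-arguments carry weight.

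- **The upper bound may not be reached.** Section 12.1 places registration after the eligibility check, and the baseline CT is timed before registration. If enrollment means registration, much of the 28 days falls before the clock starts and the lead-in is nearer 21 days. This stands: 49 days is a bound, not an expected value. The Table 1 note on the enrolment column keeps it possible.
- **One origin for both kinds of lesion is reasonable.** Atezolizumab acts on both from week 1, and a shared clock lets the two TTPs be compared. This also stands, but it argues for treatment initiation, not enrollment.
- **A clock restarted at SABR has its own costs.** It loses the shared origin and departs from the RECIST 1.1 reference. It also needs a pre-SABR scan, which is not guaranteed because CT has a ±7-day window and SABR a ±3-day window. This stands against making it the main definition.
- **The effect is small.** A shift of 2 to 5 points on an assumed 80% compares with a 95% half-width of about 11 points in 54 patients (1.96 × √(0.8 × 0.2/54)), and late scans are 12 weeks apart. This stands and limits the importance of the point.

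A reader might go further and infer that the weeks before SABR are immortal time, because a lesion counts as irradiated only once the patient reaches SABR, and that local control is therefore overstated. The documents do not support this. Section 6.4.2.1 uses the irradiated label for a lesion biopsied before atezolizumab, so it can mean a lesion planned for SABR. Nothing says whether growth at the week-4 scan counts as an event; if it does, the interval is not event-free by construction. Local control is a separate bullet in Section 7.2.1 with no definition or origin of its own, so the TTP origin cannot simply be carried over to it.

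**Conclusion.** The point holds as a mismatch of time origins. The lesion-level TTPs start at enrollment and PFS at treatment initiation, with no reason given. If enrollment opens screening, each patient's TTP contains 0 to 28 untreated days that PFS does not; if enrollment falls close to the first dose, the gap nearly vanishes. For irradiated lesions the nominal lead-in before SABR is about 21 to 49 days.

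As a measure of what follows SABR, irradiated-lesion TTP is distorted in an unknown net direction, because the lead-in and pre-SABR growth oppose each other. The medians, the 80% rate and the doubling times used for size are assumptions; the day counts come from the protocol. The endpoint is secondary and descriptive in a non-comparative trial, and no test, sample size or decision rule depends on it. This is a free improvement.

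**What to change.** In the synopsis (secondary evaluation criteria) and Sections 7.2.1 and 8.3.2, count TTP of irradiated and of non-irradiated lesions from treatment initiation, as for PFS. This removes the variable 0 to 28 days and keeps the two lesion types on one clock. About 21 days before SABR remain, by design.

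Optionally, add a supplementary descriptive analysis in patients who received SABR: time to progression of irradiated lesions from the first SABR fraction (or a week-4 landmark), with the pre-SABR scan as size reference where one exists. State how many patients lack such a scan and how progression before SABR is handled.

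The main change costs three wording edits and recalculation from dates the trial needs for PFS anyway; reported times become slightly shorter. The optional analysis adds a small amount of work and cannot include patients without a scan before SABR.
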